### 7.2 Premature Discontinuation of darTreg Infusion

darTreg infusion will be stopped and will not be restarted if there is a hypersensitivity reaction, a CTCAE Grade  $\geq$ 3 infusion-related reaction, a CTCAE Grade  $\geq$ 3 CRS, or any other infusion related serious adverse event.

Confidential Page 44 of 80

# 8. Study Mandated Procedures

# 8.1 Leukapheresis or Whole Blood Draw for PBMC Collection

Leukapheresis may be necessary to ensure collection of adequate numbers of autologous Tregs to support ex vivo expansion of darTregs for infusion after liver transplantation, particularly for those enrolled in Cohorts 3 and 4. The study team will make a decision in the best interest of a particular subject based on the current clinical picture including assigned study cohort, peripheral Tregs in circulation, and hemogloblin level. If a subject has a hemoglobin level greater than 10 gm/dL, he or she will have the option to undergo phlebotomy. If the patient has a hemoglobin level less than or equal to 10 gm/dL and remains eligible for the study, the patient will undergo leukapheresis. Number of Tregs in peripheral circulation will also guide decision for method of PBMC collection (leukapheresis or whole blood) where subjects should have at least  $30/\mu$ L peripheral blood Tregs for whole blood collection. For subjects to have whole blood draw, 450-500ml whole blood will be collected.

#### 8.2 Blood draws

Blood draws are necessary to carefully and frequently evaluate allograft function after liver transplantation as well as after darTreg infusion. Liver tests are the most reliable marker for post-transplant complications including AR. Finally, blood draws will also be done to enable the planned mechanistic studies aimed at delineating the presence and impact of infused darTregs.

# 8.3 Liver biopsies

For all subjects, local pathology information will be obtained for assessment of eligibility criteria B (no central pathology assessment). If a pathology report is unavailable from donor records, a liver biopsy will be obtained on the back table.

For patients enrolled in Cohort 1 (either 1a or 1b), there will be a second protocol liver biopsy performed 12 weeks after transplantation for central laboratory assessments.

For subjects enrolled in Cohorts 2, 3, or 4, there are two additional protocol biopsies after the initial, back table biopsy. The second protocol liver biopsy will be obtained approximately 10-14 weeks after transplantation, and approximately 7 – 10 days prior to darTreg infusion to ensure that darTregs will only be infused in the context of a normal allograft with essentially normal allograft histology and the absence of any diagnostic criteria for AR or CR. Eligibility criteria D will be assessed with local pathology information. However, slides and additional tissue will be collected for a central reading and mechanistic assays. The darTregs eligibility biopsy does not have to be repeated if a second preparation of darTregs is manufactured and infusion of the product is delayed. The third and last protocol liver biopsy for Cohorts 2, 3, or 4 will be one week after darTreg infusion for central laboratory assessments.

There will be up to two passes for each protocol biopsy. Up to one additional pass might be required during clinically indicated (standard of care) biopsies to obtain adequate tissue for the planned mechanistic studies. The same set of specimens will be collected for each 16g biopsy (protocol driven or clinically indicated/for cause) in the following priority: 1) 1.5 cm fixed in formalin for histopathology; 2) 1.5-2.0 cm in buffered saline for detection of deuterium labeled cells; 3) 0.5-1cm in RNALater for gene expression and other mechanistic studies.

Confidential Page 45 of 80

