# 10.3 Follow-up for Cohorts 1a and 1b

Participants enrolled in Cohorts 1a and 1b who will not receive darTreg infusion will follow Appendix 2. Recipient Schedule of Events (Cohort 1a and 1b) starting at week 12 after transplantation. Visits to the transplant center will take place at week 12, 16, 24 and 40 after transplantation. Laboratory assessments will take place every 4 weeks until the end of the study, 40 weeks after transplantation. Please refer to Appendix 2. Recipient Schedule of Events (Cohort 1a and 1b Follow Up)

Confidential Page 50 of 80

### 10.4 Stage 3: darTreg Infusion for Cohorts 2, 3, and 4

Participants enrolled in Cohorts 2, 3, and 4 must undergo the following study procedures and visits. darTreg infusion will take place between weeks 11-20 after liver transplantation and will require an overnight stay. Screen D eligibility must be met. Blood for central laboratory assessments will be drawn prior to the infusion and 24 hours after the infusion is complete. Visits to the transplant center will take place 1 week and 4 weeks after darTreg infusion as well as 12 and 28 weeks after darTreg infusion (approximately 24 and 40 weeks after transplantation, respectively). A liver biopsy will be done in conjunction with the visit 1 week after darTreg infusion. Thereafter, laboratory assessments must take place every two weeks for 10 weeks, followed by every 4 weeks until the end of the study, 28 weeks after darTreg infusion, or 40 weeks after transplantation. Details regarding study procedures including monitoring, laboratory assessment, and blood draws for mechanistic studies are specified in *Appendix 1. Recipient Schedule of Events (Stage 3: Cohorts 2, 3, and 4)*.

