### **Table 3. Study Visit Windows**

Stage 1 and 2 Study Visits	Visit Window
Screen A	-6 Months
Visit 1: PBMC Collection for darTreg manufacturing	Prior to transplant
Visit 2: Transplantation	-24 hours Central labs can be
	drawn up to 1 year before
	solumedrol dose in OR
Screen B	-24 hours before first dose
Visits 3a, 3b, 4, 5a, 5b: Days 3, 4, and 5 after transplantation	None
Screen C and Visits 6-15, 15a, 15b: Weeks 2-13 after transplantation	± 2 days
Cohort 1 Follow Up Study Visits	Visit Window
Visits 16: Week 12 after transplantation	-14/+10 days
Visits 17-23: Months 4-9 after transplantation	± 5 days
Stage 3 Study Visits	Visit Window
Screen D	-10 days
Visit T0: Day of darTreg Infusion	None
Visit T2: Day 1 after darTreg Infusion	± 1 hour
Visit T3: Day 7 after darTreg Infusion	± 1 day
Visit T4-T5: Day 14 and 28 after darTreg Infusion	± 2 days
Visits T6-T13: Weeks 6, 8, 10, 12, 16, 20, 24 and 28 after darTreg Infusion	± 5 days
Safety Follow Up (Early Termination from Stage 2 or 3)	Visit Window
All visits	± 7 days

Confidential Page 51 of 80

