# 11.4 Histology and Multiplex Immunohistochemistry

In collaboration with Dr. [name], we will perform extensive histology and mIHC analysis of protocol biopsy samples obtained prior to darTreg infusion and 1 week after darTreg infusion. The cohort that does not receive darTreg will get a single biopsy at 12 weeks after transplantation, the approximate time of darTreg infusion for the other groups. The design of these analyses will be guided by histology and mIHC data from tolerant patients in the [name] Immunosuppression Withdrawal trial and our current understanding of liver transplant tolerance. Histological analyses will evaluate 40 histopathological features to determine tissue integrity and degree of inflammation. mIHC analyses are summarized in *Table 4. mIHC Markers*.

Table 5. mIHC Markers

mIHC Panel	Rationale
C4d/CD31	Decrease in C4d deposits on the hepatic microvasculature is associated with liver transplant tolerance.
C40/CD31	Determine if Treg therapy leads to decrease in C4d deposits
CD3/γδ -1/ γδ -2	Portal tract ratio of $y\delta$ -1/ $y\delta$ -2 >1.0 is associated with operational tolerance. Determine if Treg therapy
CD3/y0 -1/ y0 -2	promotes this signature
CD3/CD45RO/CD45RA	Monitor the relative ratio of naïve to memory T cells; test the hypothesis that Treg therapy leads to a
CD3/CD43RO/CD43RA	reduction in portal-based CD3+/CD45RO+ (memory) T cells
CD4/Tbet/GATA-3/IL-	Monitor the polarization of CD4+ lymphocytes within the allograft to determine whether an increase of
17/FoxP3	putative Tregs contributes to tolerance.
IL10/TGFβ/HLADR	Monitor expression of immunomodulatory cytokines by HLA-DR expressing cells in the liver such as Kupffer
ILIO/ IGPP/ ILADK	and B cells.
CK19/CD31/HLADR	Up-regulation of HLA-DR on biliary epithelium (CK19+) and vascular endothelium (CD31+) makes these cells
CK13/CD31/HLADK	targets of immune rejection. Determine if Treg therapy prevents DR induction.

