8.1.1 Safety Outcome Analyses

The safety outcomes will be considered in two ways: the absolute number and the person-week incidence rates (*Section 3.2*) of selected adverse events following transplantation. The person-week incidence rate will be estimated using proportions and exact binomial two-sided 95% confidence intervals for the Safety Sample as a whole and within the two analysis periods defined above. The absolute number and the estimated incidence proportions of the following will be reported:

- Biopsy-proven acute and/or chronic rejection
- Grade ≥ 3 infections as defined in Section 13.3.1 of the Protocol
- Wound complications (\geq CTCAE Grade 3)
- Anemia, neutropenia, and/or thrombocytopenia (\geq CTCAE Grade 3)
- Adverse events attributable to the darTreg infusion including infusion reaction/cytokine releaser syndrome (\geq CTCAE Grade 3), and malignant cellular transformation.

Descriptive statistics will also be presented for:

- The severity of biopsy-proven acute and/or chronic rejection
- Reasons for termination of subjects who did not receive leukapheresis
- Use of concomitant medications

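### Rejection is looked for unequally across cohorts and analysis periods, yet SAP 8.1.1 pools protocol-biopsy and for-cause rejections in one rate

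*Protocol*

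**What the plan says.** **Biopsies.** Protocol 8.3 states for Cohorts 2 to 4 that "there are two additional protocol biopsies after the initial, back table biopsy". The first of the two is the eligibility biopsy at about weeks 10 to 14, before infusion. On the other: "The third and last protocol liver biopsy for Cohorts 2, 3, or 4 will be one week after darTreg infusion for central laboratory assessments". For Cohort 1, "there will be a second protocol liver biopsy performed 12 weeks after transplantation for central laboratory assessments", and nothing is scheduled after it. Protocol 11.4 confirms the timing: "The cohort that does not receive darTreg will get a single biopsy at 12 weeks after transplantation, the approximate time of darTreg infusion".

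**Liver tests.** Protocol 8.2 says "Liver tests are the most reliable marker for post-transplant complications including AR". Protocol 10.5 has a biopsy confirm any clinical suspicion of rejection before treatment. Protocol 10.4 sets laboratory tests after infusion every two weeks for 10 weeks and then every four weeks. Protocol 10.3 sets them every four weeks in Cohort 1.

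**Entry to the infusion period.** Criterion D10 (Protocol 4.3.5) bars infusion if the pre-infusion biopsy shows acute or chronic rejection on local reading. Protocol 15.4.1 and SAP 5 move a subject into the darTreg period only when infusion starts.

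**Analysis.** SAP 8.1.1 lists "Biopsy-proven acute and/or chronic rejection" as one item, to be given as an absolute number and a person-week rate for the Safety Sample and for two analysis periods (supportive IS; darTreg infusion). There is no split by reason for biopsy. SAP 9.5.3 counts protocol and for-cause biopsies by cohort and timepoint and lists each subject's findings. Protocol 15.4 makes all of this descriptive.

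**Week 16 in Cohort 1.** Protocol 10.3: "Visits to the transplant center will take place at week 12, 16, 24 and 40 after transplantation". Protocol Table 3: "Visits 17-23: Months 4-9 after transplantation". Appendix 2, as it reads in the text available, passes from week 12 (visit 16) to week 20 (visit 18).

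**The concern.** A biopsy-proven outcome depends on how often tissue is taken. A protocol biopsy can show rejection that no liver test had signalled; a for-cause biopsy follows only from suspicion. If the mix of the two differs between the groups or periods set side by side, a pooled rate reflects how hard rejection was looked for as well as how often it occurred.

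Here the mix does differ, and rejection is the first safety outcome. A reader will want to know whether rejection is more or less frequent after darTregs. The two natural comparisons are the darTreg period with the IS period, and the infused cohorts with Cohort 1. With 12 infused subjects and 6 in Cohort 1, one or two events found only because a protocol biopsy was scheduled can change the impression.

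**Working it through.** **1. Reproduce the plan's person-weeks.** Protocol 15.6 and SAP 3 assume 18 subjects: 6 in Cohort 1 and 12 infused (3 + 3 + 6).
- IS period: 6 × 40 + 12 × 12 = 240 + 144 = 384.
- darTreg period: 12 × 28 = 336.
- First 12 weeks only: 18 × 12 = 216.

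All agree with the plan. The 30 rows of limits in Protocol Table 8 (SAP Table 1) are reproduced by exact Poisson limits. SAP 8.1.1 names exact binomial limits, which reproduce none of the rows; that is a separate matter and does not affect this point.

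**2. Count planned protocol biopsies after transplant.** Cohort 1: 6 × 1 = 6 (week 12). Cohorts 2 to 4: 12 before infusion and 12 at day 7, so 24.

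| Comparison | Reference | Infused or darTreg | Denser in |
|---|---|---|---|
| By cohort, whole follow-up | 6/240 = 0.025 | 24/480 = 0.050 | infused cohorts (ratio 2.0) |
| By cohort, after the week-12 or pre-infusion biopsy | 0/168 | 12/336 = 0.036 | infused cohorts |
| By SAP analysis period | 18/384 = 0.047 | 12/336 = 0.036 | IS period (ratio 0.76) |

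Here 480 = 12 × 40 and 168 = 6 × 28. The third line reverses because the 12 pre-infusion biopsies fall before infusion and so belong to the IS period (6 + 12 = 18). At the maximum accrual of 24 (18 infused) it is 24/456 = 0.053 against 18/504 = 0.036, the same direction.

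**3. Effect of D10.** A rejection on the pre-infusion biopsy is counted in the IS period and bars that subject from infusion. The darTreg period therefore starts with subjects free of rejection on that biopsy, while a Cohort 1 subject with rejection at week 12 stays in the IS period. This raises the IS-period rate relative to the darTreg rate.

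**4. Scheduled liver-test time points after the reference visit** (week 12, or day of infusion).
- Infused, Appendix 3: 24 h, days 7, 14, 28, 42, 56, 70 and 84 = 8 in 12 weeks; weeks 16, 20, 24 and 28 add 4, so 12 in 28 weeks.
- Cohort 1, Protocol 10.3: weeks 16, 20 and 24 = 3 in 12 weeks; 7 in 28 weeks. Table 3 agrees: visits 17 to 23 are 23 − 17 + 1 = 7 visits.
- Cohort 1, Appendix 2 as read: 2 and 6.

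On either Cohort 1 count, infused subjects are tested more often, so for-cause biopsies have more occasions to be triggered.

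**5. How much protocol biopsies could add.** The documents give no yield per surveillance biopsy, so q is an assumption. Expected findings are n × q; the chance of at least one among 12 independent day-7 biopsies is 1 − (1 − q)^12.

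| Assumed q | Day-7 findings (12q) | Per person-week, /336 | Chance of at least one | IS-period findings (18q) | Per person-week, /384 |
|---|---|---|---|---|---|
| 5% | 0.6 | 0.0018 | 46% | 0.9 | 0.0023 |
| 10% | 1.2 | 0.0036 | 72% | 1.8 | 0.0047 |
| 20% | 2.4 | 0.0071 | 93% | 3.6 | 0.0094 |
| 30% | 3.6 | 0.0107 | 99% | 5.4 | 0.0141 |

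One added event moves the darTreg period from 0/336 (upper exact Poisson limit 0.0110) to 1/336 = 0.0030 (0.0001 to 0.0166).

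**The case against.** **The analysis is descriptive and is not a comparison with Cohort 1.** True. SAP 8.1.1 contrasts analysis periods, with no test. This limits the harm to side-by-side reading, but does not make the rates comparable: the period contrast has its own imbalance. Reading by cohort is also invited, since SAP 9.2 tabulates adverse events by cohort and Appendix 2 labels Cohort 1 visits with the matching time after infusion.

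**The data allow a split later.** SAP 9.5.3 lists biopsies and diagnoses by subject, so with about 18 subjects the split could be recovered. That stands, but it is not planned for the rejection rate.

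**Closer follow-up after a first-in-human infusion is deliberate.** Agreed. The issue is how the results are reported, not the schedule.

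A reader might go further than the documents allow in three ways.

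- *That the design is biased against darTregs.* By cohort the extra day-7 look points that way. By period, biopsy density and D10 point the other way. It is also not certain that a silent day-7 finding counts: that biopsy is for central assessment, Appendix 3 marks no local pathology result for it, and neither document says which reading makes a rejection biopsy-proven. That such findings count is inferred from unrestricted wording.
- *That one silent day-7 rejection would read as 17% to 33% (1/6 to 1/3), which Cohort 1 could never have shown.* The metric in SAP 8.1.1 is a count and a person-week rate by period, so one event is 0.0030. Cohort 1's week-12 biopsy can also show silent rejection.
- *That Cohort 1 has no week-16 visit, hence fewer liver tests and no mechanistic sample between weeks 12 and 24.* Protocol 10.3 and Table 3 include the visit. Only Appendix 2 as read omits it, and a column may have been lost when the PDF was converted. Nor does the biopsy point rest on it.

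**Conclusion.** The concern holds as one of non-comparability. Ascertainment of rejection differs by cohort (12 protocol biopsies against none after the reference biopsy; 8 scheduled liver tests against 3 in the next 12 weeks by the protocol text) and, in the opposite direction for protocol biopsies, by analysis period (0.036 against 0.047 per person-week). SAP 8.1.1 pools the two kinds of finding, so neither contrast of the pooled rate can be read as a difference in rejection risk. The net direction of bias is unknown.

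The counts assume the planned 18 subjects, full follow-up, infusion at about week 12 and every scheduled biopsy done. Subjects replaced after Thymoglobulin would change the IS-period figures. The size of the distortion cannot be derived, because it depends on a surveillance yield that the documents do not give. Since the analysis is descriptive, this is a worthwhile correction to reporting, not a fault that invalidates the trial.

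**What to change.** In SAP 8.1.1:

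1. Keep the overall count and person-week rate.
2. Add biopsy-proven rejection separately for protocol and for-cause biopsies, by cohort and analysis period, with the number of biopsies performed as denominator.
3. Show the pre-infusion (Screen D) and Cohort 1 week-12 findings together as one time-matched row.
4. Give day-7 findings their own row. They should be shown, not set aside: Protocol 5.4.3 expects product-related rejection within four weeks of infusion.
5. State whether the local or the central reading defines the event, for each type of biopsy.
6. Add a note that for-cause rates still reflect different liver-test frequency. For-cause rejections alone are therefore not a clean comparison with Cohort 1.

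Separately, check the source of Appendix 2 against Protocol 10.3 and Table 3 for week 16 (visit 17), and reconcile them if they differ.

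The cost is one further split of a planned table, from data that SAP 9.5.3 already lists, plus one rule and one appendix check. No biopsy is added. The downside is smaller counts per row.

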# 9. Known and Potential Risks and Benefits to Participants

# 9.1 Risks of Thymoglobulin® (Anti-Thymocyte Globulin – Rabbit)

Risks associated with Thymoglobulin® include immune-mediated reactions, infections, reactivation of infection, malaise, dizziness, sepsis, thrombocytopenia, neutropenia, and increased incidence of malignancies. Occasional reactions are observed at the infusion site including pain, swelling and erythema.

# Immune-mediated reactions

In rare instances, serious immune-mediated reactions have been reported with the use of Thymoglobulin and consist of anaphylaxis or severe cytokine release syndrome (CRS). Very rarely, fatal anaphylaxis has been reported. If an anaphylactic reaction occurs, the infusion should be terminated immediately. Medical personnel should be available to treat patients who experience anaphylaxis. Emergency treatment such as 0.3 mL to 0.5 mL aqueous epinephrine (1:1000 dilution) subcutaneously and other resuscitative measures including oxygen, intravenous fluids, antihistamines, corticosteroids, pressor amines, and airway management, as clinically indicated, should be provided. Thymoglobulin or other rabbit immunoglobulins should not be administered again for such patients. Severe, acute infusion-associated reactions (IARs) are consistent with CRS attributed to the release of cytokines by activated monocytes and lymphocytes. In rare instances, these reported reactions are associated with serious cardiorespiratory events and/or death. Thymoglobulin contains a mixture primarily of antibodies to T cell antigens, but it is largely unknown which specificities mediate the alteration in immunoregulation. Thymoglobulin may potentially contain or promote undesired or harmful antibody specificities, but which may be difficult to predict, identify or to exclude. Live vaccines should not be administered to patients about to receive, receiving, or after treatment with Thymoglobulin. Concomitant administration of Thymoglobulin with live virus vaccines carries a potential of uncontrolled viral replication in the immunosuppressed patient. There is insufficient information to fully define the extent of the risk, or the period of time during which the risk exists. If administered, live viruses may interfere with Thymoglobulin treatment. Skin testing is not advised prior to Thymoglobulin administration.

#### Infection

Thymoglobulin® is routinely used in combination with other IS agents. Infections (bacterial, fungal, viral and protozoal), reactivation of infection (particularly CMV) and sepsis have been reported after Thymoglobulin® administration in combination with multiple IS agents. Severe acute infections can be fatal.

# Malignancy

Use of IS agents, including Thymoglobulin®, may increase the incidence of malignancies, including lymphoma or post-transplant lymphoproliferative disease (PTLD).

# Carcinogenesis, Mutagenesis, Impairment of Fertility

The carcinogenic and mutagenic potential of Thymoglobulin® and its potential to impair fertility have not been studied.

#### **Hematologic Effects**

Thrombocytopenia and/or leukopenia (including lymphopenia and neutropenia) have been identified and are reversible following dose adjustments. When thrombocytopenia and/or leukopenia are not part of the underlying disease or associated with the condition for which Thymoglobulin is being administered, the following dose reductions are suggested:

- A reduction in dosage must be considered if the platelet count is between 50,000 and 75,000 cells/mm3 or if the white blood cell count is between 2,000 and 3,000 cells/mm3;
- Stopping Thymoglobulin treatment should be considered if persistent and severe thrombocytopenia (< 50,000 cells/mm3) occurs or leukopenia (< 2,000 cells/mm3) develops.

White blood cell and platelet counts should be monitored during and after Thymoglobulin therapy

#### Pregnancy: Pregnancy Category C

Animal reproduction studies have not been conducted with Thymoglobulin®. It is also not known whether Thymoglobulin® can cause fetal harm or can affect reproduction capacity. Thymoglobulin® should be given to a pregnant woman only if

Confidential Page 46 of 80

clearly needed. Pregnancy testing will be routinely performed in female patients pre-transplant. Although extremely unlikely, any pregnant patient will be excluded from the study.

